2.2.2 Subgroup Definitions

Certain efficacy analyses will be conducted on the various study strata. Efficacy analyses for the primary endpoints will be performed by sex (male/female), race (white/non-white), and age group (18- 34 years, 35- 64 years, and 65 year or older). Safety analyses will be grouped by treatment received.

2.3 Missing Data Conventions

Date variables with missing items will be imputed as shown in Table 2 below.

Table 2. Imputation rules for missing dates.

Data	Handling Convention
Adverse event onset date	If onset date is completely missing, impute with the date of first dose.
	If year is missing, impute with the year of enrollment.
	If only year or if year and day are present:
	
 • If year = year of first dose, then set month and day to the date of the first dose. • If year < year of first dose, then set month and day to December 31. • If year > year of first dose, then set month and day to January 1.
	If month and year are present, but day is missing:
	
 • If year = year of first dose and 
 ◦ If month = month of first dose, then set day to day of first dose.

Data	Handling Convention
Adverse event end date	
 ○ If month < month of first dose, then set day to the last day of the month. ○ If month > month of first dose, then set day to the first day of the month. • If year < year of first dose, then set day to the last day of the month. • If year > year of first dose, then set day to the first day of the month. • For all other cases, set onset date to the date of first dose.
Concomitant medications start date	
If the end date is partially or completely missing, set to the last date the subject was known to be in the study.
 
If start date is completely missing, it will not be imputed.
 
If only year or if year and day are present, set the month and day to January 1.
 
If year and month are present and day is missing, set day to the first day of the month.

Concomitant medications end date	
If end date is missing, frequency is "1X" and the medication is not listed as "ONGOING", then end date should be set to equal the start date.
 
If end date is completely missing, it will not be imputed.
 
If only year or if year and day are present, set the month and day to December 31.
 
If year and month are present and day is missing, set day to the last day of the month.

While every effort will be made to compile the data in accordance with intent-to-treat, it is likely that some subjects will have missing endpoints. Subjects with a completely missing baseline FLU-PRO[®] will have their symptoms imputed with a score of 0. Additionally, subjects who only partially complete a FLU-PRO[®] at any visit will have their missing scores imputed with a 0. Note that completely missing FLU-PRO[®] questionnaires at post-baseline visits will not be imputed.

After taking into account the imputation of missing FLU-PRO[®] scores as described above, subjects with missing primary endpoints will be imputed as uninfected. That is, subjects in both treatment arms will have their missing primary endpoint data imputed as absence of symptomatic COVID-19 disease and absence of symptomatic VRI.

Sensitivity analyses will be performed to assess the influence missing primary endpoints may have on the study's conclusions. The first analysis will be a best-case analysis, assigning infected status to all missing COVID-19 disease and VRI status in the placebo arm and non-infected status to these variables in the NTZ arm. The second sensitivity analysis will be a worst-case analysis. This analysis will assign infected status for COVID-19 disease and VRI to missing values in the NTZ arm and non-infected status to the missing values in the placebo arm. Finally, a tipping point analysis will use multiple imputation methods to determine the allocation of infected and non-infected status to missing values in the NTZ arm which changes the study conclusions.

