3. STUDY DESIGN

The study will be a multicenter, stratified, randomized, double-blind, placebo-controlled trial to evaluate the efficacy and safety of NTZ for pre- and post-exposure prophylaxis of COVID-19 and other VRIs.

Subjects will be stratified according to their most likely location of exposure, which is a proxy for exposure to SARS-CoV-2 and other VRIs. The strata are:

- Emergency Department
- Intensive Care Unit
- COVID-specific Care Unit
- Walk-in Clinic
- Paramedics and other first responders (e.g., firefighter/EMT)
- Social Activities (3-5 per week)
- Social Activities (>5 per week)

Within strata, subjects will be randomized 1:1 to one of the following groups:

- Group 1 (NTZ): Two NTZ 300 mg tablets b.i.d. for 6 weeks
- Group 2 (Placebo): Two placebo tablets b.i.d. for 6 weeks

This study is expected to run from April 2020 through April 2021.

Rationale for important issues in the study design is described below:

- *Rationale for study design.* *In vitro* data suggest NTZ may be effective against the most common viruses associated with VRIs including SARS-CoV-2. Except for influenza, there are no drugs or vaccines commercially available to prevent VRIs, especially pandemic and outbreak strains of non-influenza viruses like SARS-CoV-2. In the case of influenza these drugs are limited to only the neuraminidase inhibitors for chemoprophylaxis and the vaccine has been demonstrated to be less effective in elderly patients. This study is designed to determine if a drug with broad-spectrum antiviral activity like NTZ can prevent VRIs.

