10. ADVERSE EVENTS

The term “adverse event” is defined for purposes of this study as any unwanted physical, psychological or behavioral change experienced by a subject during the course of the study and after taking the first dose of study medication regardless of its severity or relation to the study. Adverse events may include symptoms, signs, unexpected worsening of pre-existing conditions, clinically significant changes in laboratory values, diseases and syndromes, and significant and unexpected failures of pharmacological action of other medications. Symptoms of VRIs (cough, sore throat, nasal obstruction, fatigue, headache, myalgia, feverishness) and complications of VRIs will not be reported as adverse events.

Adverse events will be recorded on the appropriate EDC forms throughout the study, and the severity of each adverse event will be graded on a four-point scale: mild, moderate, severe, or life-threatening (See [Appendix II](#)). The duration of the adverse event and relationship to the study drug will also be recorded. All adverse events must be followed until their resolution or stabilization even beyond the planned study period.

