5.2 Description of Safety Analyses

Adverse Events

Adverse events will be graded by the investigator according to the “Guidance for Industry: Toxicity Grading Scale for Healthy Adult and Adolescent Volunteers Enrolled in Preventive Vaccine Trials” as adapted in the Study Protocol. The investigator will also assess causality (relationship to treatment) as *Definitely related*, *Probably related*, *Possibly related*, and *Unrelated*. AEs will also be coded using the Medical Dictionary for Regulatory Activities version 23 or higher (MedDRA®). Treatment-emergent AEs (TEAEs), defined as any AE that occurs after a patient receives the first dose of the assigned study treatment, will be summarized by the number and proportion of patients reporting at least one occurrence of the AE. Frequencies and rates of each TEAE will be summarized by MedDRA preferred term within system organ class (SOC), by severity grade, and relation to treatment for each treatment group. The rate calculation will be based on the number of patients in the Safety population for the relevant treatment group.

Treatment emergent serious adverse events (TESAEs) will be summarized and displayed by frequency and rate by MedDRA preferred term within SOC.

A by-patient AE data listing of all adverse events including verbatim term, coded term, grade, and relation to study treatment will be provided.

Laboratory Tests

Clinical laboratory tests will be performed at the times prescribed in the protocol. The following clinical laboratory tests will be analyzed:

Hematology:

Hemoglobin, hematocrit, complete white blood count (total and differential), platelet count, random blood glucose, total cholesterol, HDL, LDL, and triglycerides.

Clinical Chemistry:

AST, ALT, GGT, alkaline phosphatase, bilirubin (total and direct), BUN, creatinine, sodium, potassium, and chloride.

Urinalysis:

Appearance, glucose, protein, and blood.

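### An adverse event recorded with a month but no year is given the enrollment year, so an early-2021 event in a subject dosed late in 2020 is dated before first dose

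*SAP*

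**What the plan says.** SAP 2.3, Table 2 sets the rules for an incomplete adverse event onset date. The relevant ones are:

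- Whole date missing: "If onset date is completely missing, impute with the date of first dose".
- Year missing: "If year is missing, impute with the year of enrollment".
- Month missing, year known: "If year = year of first dose, then set month and day to the date of the first dose". Earlier and later years go to the end or the start of that year.
- Day missing, month and year known, year equal to the first-dose year: "If month < month of first dose, then set day to the last day of the month". If the month is the first-dose month, the first-dose day is used. If it is later, the first of the month is used.
- The onset rules end with a residual line that sends any remaining case to the first-dose date.

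Protocol section 3 gives the calendar: "This study is expected to run from April 2020 through April 2021". Protocol 5.6 places the last visit at Week 8 with a window of +7 days. Protocol section 10 limits adverse events to changes "experienced by a subject during the course of the study and after taking the first dose of study medication". SAP 5.2 defines a treatment-emergent event as "any AE that occurs after a patient receives the first dose of the assigned study treatment". The five adverse event summary tables listed in SAP 8.0 (14.3.1.1 to 14.3.1.5) are all treatment-emergent tables.

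**The concern.** The trial crosses a year end, and the missing-year rule does not allow for that. Follow-up of a subject dosed in late 2020 runs into 2021, but the rule can only return 2020. A January or February event then lands some months before first dose. Under the protocol's own definition that date is impossible for an adverse event, and it also precedes the planned April 2020 start.

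The table is also inconsistent in its results. If nothing is known about the onset, or only the day, the event is placed at first dose. If the month is known as well, it can be placed almost a year too early, so more information gives a worse date.

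What is at stake is the count in the treatment-emergent tables. For post-dose events the date error goes one way, toward a pre-dose onset, so any effect on those tables is an under-count.

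**Working it through.** The documents give no figure on this point to reproduce. The check applies the Table 2 rules literally, in the order year, then month and day.

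**Inputs**

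- Year of enrollment equals year of first dose. SAP 2.2.1 counts a subject as enrolled on completion of the baseline procedures, and SAP 1.2 lists the first dose among them.
- Follow-up length L: 42 days (6-week treatment), 56 days (Week 8), or 63 days (Week 8 plus 7 days).
- First-dose dates are assumptions for illustration. The documents do not give the enrollment pattern.
- An event counts as back-dated if its imputed onset falls before first dose.

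**Example, assumed first dose 15 December 2020**

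| Recorded onset | Imputed onset | Before first dose? |
|---|---|---|
| January, no day or year | 31 Jan 2020 | yes |
| 20 January, no year | 20 Jan 2020 | yes |
| February, no day or year | 29 Feb 2020 | yes |
| 5 February, no year | 5 Feb 2020 | yes |
| Day 20 only | 15 Dec 2020 | no |
| Nothing recorded | 15 Dec 2020 | no |
| January 2021, no day | 1 Jan 2021 | no |

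Gap to first dose in the first row: 15 December is day 350 of 2020 (a leap year) and 31 January is day 31, so 350 − 31 = 319 days. The dating error itself is a different quantity. A true onset between 1 and 31 January 2021, imputed as 31 January 2020, is 336 to 366 days too early.

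**Who is exposed**

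The earliest first dose whose follow-up reaches 2021 is 1 January 2021 − L:

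- L = 56: 6 November 2020
- L = 63: 30 October 2020
- L = 42: 20 November 2020

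The last exposed first dose is 31 December 2020, with follow-up to 25 February 2021, or 4 March 2021 with the window.

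**How much of follow-up is exposed**

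Back-dated days = L − (days from first dose to 31 December 2020), with a minimum of 0. For 15 December and L = 56: 56 − 16 = 40.

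| First dose | of 42 days | of 56 days | of 63 days |
|---|---|---|---|
| 1 Nov 2020 | 0 | 0 | 3 |
| 15 Nov 2020 | 0 | 10 | 17 |
| 1 Dec 2020 | 12 | 26 | 33 |
| 15 Dec 2020 | 26 | 40 | 47 |
| 31 Dec 2020 | 42 | 56 | 63 |

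These are counts of possible onset days, not of events. Running every onset day through the rules gave the same counts whether the month alone or the month and day were recorded, and the back-dated days were exactly the 2021 days. With only the day recorded, none was back-dated. First doses on 1 July 2020, 1 October 2020 and 5 January 2021 gave none.

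**The case against.** The strongest objection rests on the residual line. If it governs the whole onset row, a record with month but no year fits none of the listed patterns, goes to the first-dose date and stays treatment-emergent. The table's layout does not settle its scope. But that reading would send every missing-year record to first dose and leave the year-of-enrollment rule with nothing to do. The rule has an effect only if the year is filled in first and the month and day rules follow. What stands is that the order is not written down, and it should be.

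The second objection stands as a limit. The SAP does not say that the treatment-emergent flag uses the imputed date. If every recorded adverse event is taken as post-dose under the protocol definition, the date is wrong but the count is not.

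The third concerns safeguards. Protocol 7.1 provides for queries and cleaning before lock, and Protocol 11.1 for adverse event listings at least every two weeks during recruitment. An onset before the planned start is easy to see. This bears on how many such records survive, not on whether the rule is right.

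A reader might also infer more than the documents support:

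- *That all missing-year events are affected.* Those with the month also missing go to first dose and are kept.
- *That the events at risk are all on treatment.* For first doses before about 20 November 2020, every 2021 day falls after the 6-week treatment period. For 15 December, 26 of the 40 days are on treatment.
- *That the rule defeats a conservative purpose of the table.* The SAP states no such purpose, and other rules in the row deliberately give pre-dose dates when the recorded year or month is earlier.

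**Conclusion.** Wrong as written, minor. On the sequential reading, the missing-year rule gives an impossible onset date for any early-2021 event recorded with a month but no year in a subject first dosed between about 6 November (30 October with the visit window) and 31 December 2020. This rests on the planned calendar and on the year being filled in before the month and day rules apply.

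The further step, that such events could be missing from Tables 14.3.1.1 to 14.3.1.5, also assumes that the flag is computed from the imputed date. It should be put as a possibility. Even then the events remain visible in Listing 16.2.7.1.

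The documents give neither the number of late-2020 enrollees nor the frequency of missing years. The number of affected records is probably small. A reader might infer that the rule favors nitazoxanide by hiding events. The documents do not support that, because the rule is the same in both arms and nothing suggests that missing years differ between them.

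**What to change.** Replace the missing-year line in SAP Table 2 with:

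> If year is missing and month is present, use the year (enrollment year or the next) that puts the onset on or after first dose and on or before the last date in the study; if neither does, use the date of first dose. Apply this step before the month and day rules.

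Follow-up is far shorter than a year, so at most one of the two years can fit. For month-only records, the test is whether any day of that month lies in the interval. In the example, a January onset with no day or year becomes January 2021, and the existing day rule sets 1 January 2021. No event is then imputed before first dose.

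It would also help to add a sentence to SAP 5.2 saying whether the treatment-emergent flag uses the imputed onset date, and to count the records with month present and year missing, pooled over arms, so that the actual effect is known.

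The cost is one line in the SAP and one line of code. No new data are needed.

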4.0 Analysis of Efficacy

4.1 Efficacy Variables

All the efficacy variables are categorical in nature: the presence or absence of any VRI, ARI, or COVID-19 during the study period. Similarly, hospitalization (and its cause) and death (and its cause) are categorical.

Primary Efficacy Variables

There are two primary efficacy variables:

1. The presence or absence of symptomatic COVID-19 disease identified after the start of treatment and before the end of the 6-week treatment period.
2. The presence or absence of symptomatic VRI (including COVID-19) identified after the start of treatment and before the end of the 6-week treatment period.

Symptomatic COVID-19 is defined as an ARI after start of treatment and before the end of the 6-week treatment period associated with detection of SARS-CoV-2 by RT-PCR assay of nasopharyngeal swab.

Symptomatic VRI is defined as an ARI after start of treatment and before the end of the 6-week treatment period associated with detection of any respiratory virus by RT-PCR assay of nasopharyngeal swab.

A subject will be considered to have met the criteria for an ARI if:

1. The subject meets the criteria that trigger the Suspected ARI Visit (see Section 1.2);

AND

2. The subject satisfies the following ARI definition: ARI is defined as ≥ 0.5 increase from baseline in mean symptom score for the FLU-PRO[®] chest/respiratory domain alone; or a ≥ 0.5 increase from baseline in mean symptom score for at least two of the following FLU-PRO[®] domains: body/systemic, nose, throat.

Secondary Efficacy Variables

The secondary efficacy variables are:

1. Mortality due to COVID-19 or complications thereof.
2. The presence or absence of anti-SARS-CoV-2 antibodies at either of the Week 6 or Week 8 visits.

Exploratory Efficacy Variables

The exploratory efficacy variables are:

1. Hospitalization due to VRI or complications thereof.
2. Mortality due to VRI or complications thereof.
3. Presence or absence of an ARI.
4. Hospitalization due to ARI or complications thereof.
5. Mortality due to ARI or complications thereof.

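### SAP 2.3 scores unanswered FLU-PRO items as 0, which raises the effective ARI cut-off for partly completed illness diaries, and no planned sensitivity analysis tests it

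*SAP*

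**What the plan says.** SAP 2.3 sets four rules, applied in order:

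- A wholly missing baseline FLU-PRO: the subject "will have their symptoms imputed with a score of 0".
- A partly completed FLU-PRO: subjects "at any visit will have their missing scores imputed with a 0". This covers baseline and illness diaries alike.
- A wholly missing later form: such "questionnaires at post-baseline visits will not be imputed".
- After these steps, "subjects with missing primary endpoints will be imputed as uninfected", in both arms.

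The best-case, worst-case and tipping-point analyses are there "to assess the influence missing primary endpoints may have" on the conclusions.

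SAP 4.1 builds both primary endpoints on an ARI. The first condition is "The subject meets the criteria that trigger the Suspected ARI Visit". The second is a rise of at least 0.5, either as an "increase from baseline in mean symptom score for the FLU-PRO" chest/respiratory domain, or as a "0.5 increase from baseline in mean symptom score for at least two of the following" domains: body/systemic, nose and throat. A counted case also needs a positive nasopharyngeal RT-PCR. Protocol 8.3 gives the same 0.5 cut-off, and the protocol has no rule for unanswered items.

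**The concern.** Scoring a blank item as symptom-free treats lack of an answer as evidence of health. In an illness diary this pulls the domain mean down and raises the cut-off for anyone who leaves items blank. The protocol's rationale for the ARI definition (section 3) describes the required rise as deliberately low; zero-fill makes it higher for incomplete forms only.

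The result is also hidden. A status computed from zero-filled items is not missing, so it passes through every planned analysis unchanged. The treatment is uneven as well. If a wholly blank illness form leaves the endpoint missing, the sensitivity analyses vary that endpoint. A form with one answered item is scored as if every other symptom were absent, and nothing varies it.

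Both primary endpoints pass through this score and the trial is sized on 24 COVID-19 cases, so lost cases cost information directly.

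**Working it through.** **1. The plan's own figure.** Inputs from SAP 1.3 and 4.2.1: COVID-19 rate 1%, taken here as the placebo rate; 80% reduction, so 0.2% on NTZ; two-sided alpha 0.049; power 90%; 1:1 allocation. With pooled rate p̄ = 0.006,

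n per arm = [z(0.0245)·√(2p̄(1−p̄)) + z(0.10)·√(p1(1−p1) + p2(1−p2))]² / (p1−p2)²

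= [1.9685 × 0.10922 + 1.2816 × 0.10907]² / 0.008² ≈ 1,967, or 3,934 in total. The plan states approximately 4,000, so the base case reproduces. Power at 4,000 is 90.5%.

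**2. Effective cut-off after baseline.** For a domain of k items with m unanswered,

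zero-filled mean = answered-item mean × (k−m)/k.

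From a zero baseline, reaching 0.5 needs an answered-item mean of at least 0.5/(1−f), where f = m/k:

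| Share unanswered (f) | Answered items must average |
|---|---|
| 0 | 0.50 |
| 1/4 | 0.67 |
| 1/3 | 0.75 |
| 1/2 | 1.00 |

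With a single blank item, the cut-off is 0.75 in a 3-item domain and 0.55 in an 11-item domain. The documents do not give the number of items per domain, so that range is assumed. As an example, take an assumed 5-item domain with two blanks and answers 1, 1, 0. The answered-item mean is 2/3 = 0.67 (qualifies); the zero-filled mean is 2/5 = 0.40 (does not).

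**3. Partly completed baseline.** The error reverses. Suppose the true baseline mean is 0.4, half the items are blank so that it is recorded as 0.2, and the illness mean is 0.8. The true rise is 0.4; the scored rise is 0.6. To count on a primary endpoint, this subject must also meet the symptom trigger and have a positive PCR.

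**4. Reach of the sensitivity analyses.** SAP 2.3 defines a missing endpoint after the FLU-PRO fill. A zero-filled form yields a computed change, hence a non-missing status. All three sensitivity analyses act on missing statuses only, so none changes it.

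**5. What lost cases would cost.** The share of true cases lost is an assumption, taken as equal in both arms. Both rates are multiplied by s = 1 − loss. Expected events at 4,000 are 4,000 × 0.006 × s, and the N that yields 24 events is 24/(0.006 × s).

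| Cases lost | Expected events at 4,000 | Power at 4,000 (formula of step 1) | Power at 4,000 (simulated 7-stratum CMH, continuity corrected) | N for 24 events |
|---|---|---|---|---|
| 0 | 24.0 | 90.5% | 90% | 4,000 |
| 5% | 22.8 | 89.0% | 88% | 4,211 |
| 10% | 21.6 | 87.3% | 85% | 4,445 |
| 20% | 19.2 | 83.2% | 80% | 5,000 |
| 30% | 16.8 | 78.0% | 74% | 5,715 |

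The trial is event-driven, so modest losses appear first as more subjects needed. On these rates, any loss pushes the N for 24 events above the protocol's 4,000 maximum.

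**6. Sensitivity to single cases.** Unstratified CMH with continuity correction, 2,000 per arm. Of 24 events, the design effect puts 4 on NTZ and 20 on placebo: 4 v 20 gives p = 0.002, and losing one placebo case (4 v 19) gives p = 0.003. Seven placebo cases and no NTZ case must be lost before significance at 0.049 fails (4 v 13, p = 0.052).

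**The case against.** The case for leaving the rule alone has real substance.

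- **Partial forms may be rare.** The diary is electronic, and site staff review it daily and contact subjects about incomplete entries (protocol 5.3). The documents do not say whether the device allows an item to be skipped. This stands: the frequency is unknown and may be small.
- **One partial entry need not lose a case.** Illness diaries repeat daily until recovery, SAP 4.1 names no single qualifying day, and an ARI can be met through chest/respiratory alone or any two of three other domains. With a quarter of items blank, only answered-item means from 0.5 up to 0.67 are reclassified. This stands as a limit on size.
- **The rule is the same in both arms.** It should mainly cost events, unless completeness differs by arm. This also stands.

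Three stronger readings are tempting, and the documents do not support them. A reader might infer that zero-filled baselines turn well people into primary-endpoint cases. They do not: the symptom trigger and a positive PCR are still required. The inflated rise bears more on the exploratory ARI endpoint, which needs no PCR. A reader might infer that true cases are certainly being lost because ill subjects leave diaries unfinished. That is plausible, but nothing in the documents shows it. A reader might also infer that a single misclassified case would decide the trial. One can at a knife-edge split (7 v 17 gives p = 0.065; 6 v 17 gives p = 0.037), but that is true of any endpoint near its boundary, and at the design split one lost case barely moves the result.

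None of this makes zero the right score for an unanswered illness item, or brings the affected subjects within any planned sensitivity analysis.

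**Conclusion.** The concern holds for partly completed forms. After baseline, the stated rule biases domain means downward, raises the effective cut-off from 0.5 to between 0.67 and 1.0 when a quarter to a half of the items are blank, and can fix a symptomatic, PCR-positive subject as a non-case in every planned analysis. The opposite bias from a partly completed baseline is real but narrow for the primary endpoints.

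The size cannot be established, because the partial-completion rate, the item counts and the item scale are not given. The expected consequence is fewer events and lower power in both arms, on the scale of step 5 if the assumed losses occurred. This is not evidence of a false-positive result.

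The concern does not extend to replacing zero for a wholly missing baseline in the primary analysis. The baseline diary is completed under supervision, and recent respiratory infection and active respiratory allergy are exclusions, so zero is defensible there. Removing it would leave such subjects without a change score, and SAP 2.3 would then count them as uninfected even if symptomatic and PCR-positive.

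**What to change.** Amend SAP 2.3 before unblinding:

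1. At baseline and afterwards, score each FLU-PRO domain as the mean of the answered items when at least half are answered, or by the instrument's own scoring rule if it has one. The half-answered threshold is a convention; the instrument's scoring rule is not in the documents.
2. Otherwise treat that domain as missing for that day. State that an endpoint left undetermined as a result counts as a missing primary endpoint, so that it enters the existing best-case, worst-case and tipping-point analyses.
3. Keep item-level zero-fill as a sensitivity analysis.
4. Keep zero for wholly missing baselines in the primary analysis, and add a sensitivity analysis that varies it.
5. Report the number of partly completed forms by arm, so that the size of the problem is visible.

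The cost is SAP wording and minor programming, with no new data. The downside is a few domain-days set to missing; in the primary analysis an undetermined endpoint would still count as uninfected, but the sensitivity analyses would now vary it.
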